### 8.1.1.2 Serious Adverse Events

If an AE meets any of the criteria outlined in [Table 8-1](#), the AE is to be reported to AbbVie as an SAE within 24 hours of the site being made aware of the SAE.

**Table 8-1 Criteria for a Serious Adverse Event (SAE)**

Death of Subject	An event that results in the death of a subject.
Life Threatening	An event that, in the opinion of the Investigator, would have resulted in immediate fatality if medical intervention had not been taken. This does not include an event that would have been fatal if it had occurred in a more severe form.
Hospitalization or Prolongation of Hospitalization	An event that results in an admission to the hospital for any length of time or prolongs the subject's hospital stay. This does not include an emergency room visit or admission to an outpatient facility, or hospitalization for respite care.
Congenital Anomaly	An anomaly detected at or after birth, or any anomaly that results in fetal loss.
Persistent or Significant Disability/Incapacity	An event that results in a condition that substantially interferes with the activities of daily living of a study subject. Disability is not intended to include experiences of relatively minor medical significance such as headache, nausea, vomiting, diarrhea, influenza, and accidental trauma (e.g., sprained ankle).
Important Medical Event Requiring Medical or Surgical Intervention to Prevent Serious Outcome	An important medical event that may not be immediately life threatening or result in death or hospitalization, but based on medical judgment may jeopardize the subject and may require medical or surgical intervention to prevent any of the outcomes listed above (i.e., death of subject, life threatening, hospitalization, prolongation of hospitalization, congenital anomaly, or persistent or significant disability/incapacity). Additionally, any elective or spontaneous abortion or stillbirth is considered an important medical event. Examples of such events include allergic bronchospasm requiring intensive treatment in an emergency room or at home, blood dyscrasias or convulsions that do not result in inpatient hospitalization, or the development of drug dependency or drug abuse.

Note: For SAEs with the outcome of death, the date and cause of death will be recorded on the appropriate CRF.

### 8.1.1.3 Adverse Events Expected Due to Cancer Progression

The term "disease progression" alone should not be used when reporting AEs or SAEs, due to its lack of specificity. Rather, symptoms of disease progression (PD) should be collected under the unifying diagnosis of "malignant neoplasm progression;" symptoms of progression may be subsumed under this diagnosis.

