## 1.4 Rationale for the Study and Anticipated Risks

Rovalpituzumab tesirine may be effective in multiple cancers that express DLL3. This study will explore further the safety, tolerability, and potential therapeutic utility of rovalpituzumab tesirine in subjects with such non-SCLC DLL3+ tumors, with the intent to provide the basis for further development of rovalpituzumab tesirine in one or more of these evaluated indications.

As of 30 June 2016, 104 subjects (SCLC or LCNEC) had received at least one dose of rovalpituzumab tesirine at doses ranging from 0.05 mg/kg to 0.8 mg/kg on an every 3 weeks (Q3wk) schedule (34 subjects) and 0.3 mg/kg to 0.4 mg/kg on an every 6 weeks (Q6wk) schedule (70 subjects).

The most frequently reported treatment-emergent adverse event (TEAE) terms in all treated subjects were fatigue (49%), pleural effusion (34%), and dyspnea (31%); the most frequently reported TEAE terms considered related to rovalpituzumab tesirine by the Investigator were fatigue (35%), pleural effusion (28%), and peripheral edema (26%).

The most frequently reported Grade 3/4 TEAEs were dyspnea (14%), pleural effusion (12%), and fatigue (11%); the most frequently reported Grade 3/4 TEAEs considered related to rovalpituzumab tesirine were pleural effusion and thrombocytopenia (10% each), and fatigue and increased lipase (6% each).

Serious adverse events (SAEs) were reported in 49 subjects (47%), 26 (25%) were considered related to rovalpituzumab tesirine by the Investigator. The most common SAE was pleural effusion, occurring in 18 subjects (17%); all occurrences were considered related to rovalpituzumab tesirine. The second most common related SAE was pericardial effusion, in 8 subjects (8%). Six subjects experienced a fatal AE, 2 of which were considered related to rovalpituzumab tesirine (acute kidney injury and tumor hemorrhage).

Preclinical toxicology studies conducted in the rat and the cynomolgus monkey have identified the bone marrow, lung, and kidney as a potential source of clinical adverse events (AEs) (refer to Section 4.3.1 of the current Rovalpituzumab Tesirine Investigator's Brochure [IB]; Stemcentrx data on file). Accordingly, safety assessments will include regular assessments at protocol-specified time points of routine physical examination, laboratory and imaging tests, as well as echocardiograms (ECHOs), a fluid retention questionnaire, daily weights, and untimed (spot) analysis of protein.

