### **3.2.4 Blinding**

This is not a blinded trial.

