#### 8.1.1 Definitions

##### 8.1.1.1 Adverse Events

An AE is defined as any untoward medical occurrence in a patient or clinical investigation subject administered a pharmaceutical product and which does not necessarily have a causal relationship with this treatment. An AE can therefore be any unfavorable and unintended sign (including an abnormal laboratory finding), symptom, or disease temporally associated with the use of a medicinal (investigational) product, whether or not the event is considered causally related to the use of the product.

Such an event can result from use of the drug as stipulated in the protocol or labeling, as well as from accidental or intentional overdose, drug abuse, or drug withdrawal. Any worsening of a pre-existing condition or illness is considered an AE.

Worsening in severity of a reported AE should be reported as a new AE. Laboratory abnormalities and changes in vital signs are considered to be AEs only if they result in discontinuation from the study, necessitate therapeutic medical intervention (including interruption/dose reduction of study drug, starting or discontinuing medication, etc.), meets protocol specific criteria (refer to Sections 5.5 and 8.1 regarding toxicity management) and/or if the Investigator considers them to be AEs.

An elective surgery/procedure scheduled to occur during a study will not be considered an AE if the surgery/procedure is being performed for a pre-existing condition and the surgery/procedure has been pre-planned prior to study entry. However, if the pre-existing condition deteriorates unexpectedly during the study (e.g., surgery performed earlier than planned), then the deterioration of the condition for which the elective surgery/procedure is being done will be considered an AE.

All protocol-related AEs must be collected from the signing of the study specific informed consent until study drug administration.

In addition, AEs with onset or worsening reported by a subject from the time that the first dose of study drug is administered until 70 days have elapsed following discontinuation of study drug administration will be considered as TEAEs.

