### **8.2.3 Events Commonly Associated in Study Population with Advanced Solid Tumors and/or Progression of Underlying Malignancy**

Certain AEs are anticipated to occur in the study population at some frequency independent of drug exposure. Such events include known consequences of the underlying disease or condition under investigation (e.g., symptoms, PD).

A list of AEs associated with advanced solid tumors is provided in [Appendix 13.10](#). These AEs are preferred terms coded according to the latest version of the Medical Dictionary for Regulatory Activities (MedDRA) dictionary; the AEs may occur alone or in various combinations and are considered expected for reporting purposes for this protocol. Although exempted from expedited reporting to Health Authorities and IRBs as individual cases, if these AEs meet serious criteria these SAEs must be reported to AbbVie within 24 hours of the site

being made aware of the SAE (as required in [Section 8.1.6](#)). For deaths related to disease progression (coded to malignant neoplasm progression), the date and cause of death will be recorded on the appropriate case report form (CRF), but the event will not be expedited as an Individual Case Safety Report (ICSR) to regulatory authorities ([Section 8.1.4](#)).

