### **10.3.7.1 Treatment Emergent Adverse Events**

TEAEs reported during the study will be coded using a Medical Dictionary for Regulatory Activities (MedDRA) dictionary. Incidence of TEAEs will be summarized by disease and cohort and the following:

- System organ class and preferred term
- System organ class, preferred term and severity

These summaries will be presented for the following subsets:

- Serious adverse events
- All adverse events
- Drug-related adverse events
- Adverse events leading to treatment discontinuation

For tables reporting AEs by severity, if a subject has multiple occurrences of an AE with the same organ class and preferred term, the most severe event will be presented.

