### 13.10 Disease Related Events Associated with Solid Tumors

Abdominal pain  
Asthenia  
Back pain  
Bone pain  
Cough  
Decreased appetite  
Deep vein thrombosis  
Dysphagia  
Dysphonia  
Dyspnea  
Esophageal obstruction  
Fatigue  
General physical health deterioration  
Horner's syndrome  
Ileus  
Infection\*  
Jaundice  
Lymphadenopathy  
Malaise  
Malignant pleural effusion  
Malignant ascites  
Metastasis  
Nausea  
Non-cardiac chest pain  
Opportunistic infection\*  
Paraneoplastic syndrome  
Pathological fracture  
Pneumonia\*  
Pruritus  
Pulmonary embolism  
Pyrexia  
Sepsis\*  
Septic shock\*  
Small intestinal obstruction  
Superior vena cava syndrome  
Tumor pain  
Vocal cord paralysis  
Vomiting  
Weight decreased

\* Includes life threatening or fatal events.

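### Symptoms attributed to progression can be recoded to a single progression term, which can lower the by-term rates of dyspnea and, to a lesser extent, effusions

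*Combined protocol and SAP*

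**What the plan says.** Section 8.1.1.3 tells sites to gather symptoms of progression under one diagnosis, malignant neoplasm progression, and then states that "symptoms of progression may be subsumed under this diagnosis". It gives no criterion for attributing a symptom to progression, does not ask for a scan or cytology, and does not ask that the symptom also be kept as its own record.

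Section 8.1.1.1 defines an AE regardless of cause: "whether or not the event is considered causally related to the use of the product". Section 2.1 makes safety and tolerability the primary objective, and Section 3.2.4 says "This is not a blinded trial".

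Section 10.3.7.1 sets the tables: "Incidence of TEAEs will be summarized by disease and cohort and the following" (system organ class and preferred term, then the same by severity). These are given for serious, all, drug-related and discontinuation AEs.

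Section 8.2.3 and Appendix 13.10 list disease-related events as individual preferred terms. Section 8.2.3 says "the AEs may occur alone or in various combinations and are considered expected for reporting purposes for this protocol". The list contains dyspnea, fatigue, "Malignant pleural effusion" and malignant ascites. It does not contain plain pleural effusion, pericardial effusion or edema.

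Section 5.5.1, on serosal effusions, asks that progression and other causes be ruled out, with cytology as appropriate for pleural and pericardial effusions. It also prefers a unifying diagnosis over the sign, when appropriate.

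**The concern.** Dyspnea and effusions can come from the drug or from the tumor. With no control arm, the usual protection against wrong attribution is the all-causality rate for each preferred term: it counts the event whatever the investigator thinks caused it. Under Section 8.1.1.3 the attribution comes first and decides which term is recorded. A dyspnea attributed to progression may then have no dyspnea row and no dyspnea grade. The by-term rate that should be independent of attribution becomes partly dependent on it.

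This touches events of known concern. In Section 1.4, pleural effusion was the second most frequent TEAE both overall and among related events, and the most common SAE (18 of 104 subjects, all judged related). Dyspnea was third overall and first at Grade 3/4, although it is not among the leading related terms. Disease-specific cohorts are planned at about 25 subjects at the recommended dose, so a few recoded events would change a rate visibly.

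Sites are also left with two signals. Section 8.1.1.3 points to one term, while Section 8.2.3 and Appendix 13.10 treat dyspnea, malignant pleural effusion and malignant ascites as terms that may stand alone.

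**Working it through.** The plan states no design figure on this point, so there is none to reproduce. The check uses the safety figures in Section 1.4 (n = 104, SCLC or LCNEC).

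**Consistency of the source figures.** Where Section 1.4 gives both a count and a percentage, they agree: 49/104 = 47.1% (stated 47%), 26/104 = 25.0% (25%), 18/104 = 17.3% (17%), 8/104 = 7.7% (8%). Each percentage used below corresponds to only one whole number out of 104.

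**Subjects whose event was counted as not related** (any-cause minus related):

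| Event | Any cause | Related | Not related |
|---|---|---|---|
| Pleural effusion | 34% = 35 | 28% = 29 | 35 − 29 = 6 (6/35 = 17%) |
| Dyspnea | 31% = 32 | at most 26% = 27 | at least 32 − 27 = 5 (5/32 = 16%) |
| Grade 3/4 pleural effusion | 12% = 12 | 10% = 10 | 12 − 10 = 2 (2/12 = 17%) |
| Grade 3/4 dyspnea | 14% = 15 | at most 6% = 6 | at least 15 − 6 = 9 (9/15 = 60%) |

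The caps for dyspnea arise because it is absent from the lists of most frequent related terms. The lowest rate shown there is 26% at any grade and 6% at Grade 3/4, so related dyspnea cannot exceed those values. The two dyspnea differences are therefore minimums of the not-related count.

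**What these counts mean.** They show how many subjects fell in the group most open to recoding. They do not show how many would be recoded, because Section 1.4 does not say how many not-related events were attributed to progression. Infection, heart failure or another illness would also be counted as not related, and Section 8.1.1.3 does not cover those.

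**Illustration for a cohort of 25.** Assume the Section 1.4 rates apply, and let the fraction of the (minimum) not-related share that is recoded run from 0 to 1. The expected number of subjects in the symptom's own row is:

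- Grade 3/4 dyspnea: 25 × 0.14 = 3.5, falling to 25 × 0.06 = 1.5
- Dyspnea, any grade: 25 × 0.31 = 7.8, falling to 25 × 0.26 = 6.5
- Pleural effusion: 25 × 0.34 = 8.5, falling to 25 × 0.28 = 7.0

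The chance that a cohort of 25 shows no Grade 3/4 dyspnea at all would rise from 0.86^25 = 0.023 to 0.94^25 = 0.213 at the far end of that range.

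**The case against.** The strongest reply is that nothing is lost: Section 8.1.1.3 has the symptoms recorded under the progression term, and Section 10.3.7.1 tabulates by preferred term, so the event stays in the all-causality tables in a visible row. That stands. A reader might infer that such events go unrecorded; the text does not support this. What changes is the term and grade under which they appear.

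Second, effusions are not left to bare judgment, since Section 5.5.1 asks that progression be ruled out. That also stands in part and is why the point is weaker for effusions than for dyspnea. It does not close the gap: cytology is only as appropriate, and the section itself favors a unifying diagnosis.

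Third, the list in Section 8.2.3 and Appendix 13.10 serves expectedness and expedited reporting, names effusions only as malignant, and omits pericardial effusion. So this is an unreconciled inconsistency, clearest for dyspnea, and not a flat contradiction.

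Fourth, dyspnea and edema are asked about in the fluid retention questionnaire, and pericardial effusion is looked for on echocardiogram. These are separate safety endpoints. They limit what could be missed, but they do not restore the preferred-term rates.

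Three further inferences are tempting and are not supported. The primary safety assessment is not necessarily biased downward, since the amount recoded may be nil and other safety endpoints exist. Lack of comparability with the sponsor's previous studies cannot be claimed, because the documents do not say how those studies recorded symptoms of progression. And Section 10.3.7.1 plans no table of fatal AEs, so there is no planned fatal total to distort.

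**Conclusion.** The point holds as a cheap improvement. Section 8.1.1.3 lets investigator attribution, in an open-label trial without a control arm, move dyspnea and to a lesser extent effusions out of their own term and grade rows, which can lower the all-causality rates by term. It is not reconciled with Section 5.5.1, Section 8.2.3 or Appendix 13.10.

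The size is not known. The not-related counts in the 104 prior subjects mark the exposure, and the share moved could lie anywhere from none to all of them. Exposure is proportionately largest for Grade 3/4 dyspnea (at least 60% not related, against 17% for pleural effusion).

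This rests on two assumptions: that the lists of most frequent related terms in Section 1.4 are complete down to the lowest rate shown, and, for the cohort illustration, that rates in SCLC and LCNEC carry over to the tumor types studied here, which the documents do not establish.

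**What to change.** - **Section 8.1.1.3:** require that pleural and pericardial effusion, ascites, edema, dyspnea and pneumonitis always be recorded as their own AE, with grade and onset, even when attributed to progression, and add a suspected-progression flag to the record. Pneumonitis belongs here because Section 5.5.5 names underlying cancer among the confounders of the reported cases.
- **Sections 8.1.1.3, 5.5.1 and 8.2.3, and Appendix 13.10:** reconcile the wording, so that sites have one recording rule and the Appendix 13.10 list is clearly an expectedness list.
- **Section 10.3.7.1, or the SAP to which Section 10 leaves further detail:** present the TEAE, SAE and discontinuation tables with and without the preferred term malignant neoplasm progression.

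The cost is protocol and CRF-guideline wording, some extra AE records around the time of progression, and one repeat of existing tables. The change concerns recording and reporting only. It should be made prospectively, because symptoms not recorded at the time may be hard to recover.

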### 8.1.2 Adverse Event Severity

The Investigator will rate the severity of each AE according to the NCI CTCAE v4.03. If a reported AE **increases** in severity, the initial AE should be given an outcome date and a new AE reported on a different date from the end date of the previous AE to reflect the change in severity. For all reported SAEs that increase in severity, the supplemental eCRFs also need to be updated to reflect the change in severity.

When CTCAE criteria cannot be used, the event should be graded as defined below:

- Grade 1**        The adverse event is transient and easily tolerated by the subject (mild).
- Grade 2**        The adverse event causes the subject discomfort and interrupts the subject's usual activities (moderate).
- Grade 3/4**      The adverse event causes considerable interference with the subject's usual activities and may be incapacitating or life threatening (severe).
- Grade 5**        The adverse event resulted in death of the subject (severe).

### 8.1.3 Relationship to Study Drug

The Investigator will use the following definitions to assess the relationship of the AE to the use of study drug:

- Reasonable Possibility**      After consideration of factors, including timing of the event, biologic plausibility, clinical judgment, and potential alternative causes, there is **sufficient** evidence (information) to suggest a causal relationship.
- No Reasonable Possibility**    After consideration of factors, including timing of the event, biologic plausibility, clinical judgment, and potential alternative causes, there is **insufficient** evidence (information) to suggest a causal relationship.

For causality assessments, events assessed as having a reasonable possibility of being related to the study drug will be considered "associated." Events assessed as having no reasonable possibility of being related to study drug will be considered "not associated." In addition, when the Investigator has not reported a causality or deemed it not assessable, AbbVie will consider the event associated.

If an Investigator's opinion of no reasonable possibility of being related to study drug is given, an "Other" cause of event must be provided by the Investigator for the SAE.

#### **8.1.4 Deaths**

For SAEs with the outcome of death, the date and cause of death will be recorded on the appropriate case report form.

Deaths that occur during the protocol specified AE reporting period ([Section 8.1.5](#)) that are more likely related to PD will therefore be considered as an expected AE and will not be subject to expedited reporting to regulatory agencies. These SAEs should be reported as "malignant neoplasm progression" and also recorded on the AE eCRF. After the AE reporting period, deaths attributed to PD under study should be recorded only on the end of study (EOS) eCRF.

Death should be considered an outcome and not a distinct event. The event or condition that caused or contributed to the fatal outcome should be recorded as the single medical concept on the AE eCRF. Generally, only one such event should be reported. The term "sudden death" should only be used for the occurrence of an abrupt and unexpected death due to presumed cardiac causes in a patient with or without pre-existing heart disease, within 1 hour of the onset of acute symptoms or, in the case of an unwitnessed death, within 24 hours after the patient was last seen alive and stable. If the cause of death is unknown and cannot be ascertained at the time of reporting, "unexplained death" should be recorded on the AE eCRF. If the cause of death later becomes available (e.g., after autopsy), "unexplained death" should be replaced by the established cause of death.

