### 3.1.3 Definition of Dose-Limiting Toxicities

The DLT evaluation period is the first 3 weeks of the first cycle of treatment for all subjects in Part A. DLTs are defined as any of the following in the DLT evaluation period, graded according to the National Cancer Institute’s Common Terminology Criteria for Adverse Events (NCI CTCAE), version 4.03:

- Grade 4 thrombocytopenia (or Grade 3 thrombocytopenia with bleeding) lasting more than 7 days and/or requiring platelet transfusion
- Grade 4 neutropenia lasting more than 7 days, and/or requiring hematopoietic growth factor rescue, or any febrile neutropenia (Grade 3 or 4 neutropenia with concurrent fever  $\geq 38.3^{\circ}\text{C}$ )
- Grade 4 anemia unrelated to underlying disease
- Clinically-significant Grade 3 or 4 non-hematologic laboratory abnormality that does not resolve to Grade 0/1 or baseline within 7 days
- Grade 3 or 4 non-laboratory AE with the exception of fatigue, asthenia, nausea, or other manageable constitutional symptom

The following events will not be considered DLTs:

- Any AE  $\geq$  Grade 3 clearly determined to be unrelated to study drug (e.g., PD)
- $\geq$ Grade 3 isolated alkaline phosphatase, amylase or lipase laboratory abnormality of any duration

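### Section 8.1.4 gives deaths that are more likely due to progression the progression term and an expedited-reporting exemption whatever their causality rating under Section 8.1.3, so a drug-associated death can be recorded under a term that hides the toxicity

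*Combined protocol and SAP*

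**What the plan says.** Section 8.1.4 governs deaths in the AE reporting period, which Section 8.1.5 runs to 70 days after study drug is discontinued. Deaths "that are more likely related to PD will therefore be considered as an expected AE", and they are not expedited to regulators. On the term to use: "These SAEs should be reported as 'malignant neoplasm progression' and also recorded on the AE eCRF". The section does not say what progression must be more likely than, and it does not mention the causality rating. It also says that the condition behind a death, or contributing to it, "should be recorded as the single medical concept on the AE eCRF. Generally, only one such event should be reported".

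Section 8.1.3 sets the causality rating: "events assessed as having a reasonable possibility of being related to the study drug will be considered" associated. The definition of a reasonable possibility opens "After consideration of factors, including timing of the event, biologic plausibility, clinical judgment, and potential alternative causes, there is" and then requires sufficient evidence pointing to a causal link. If the investigator gives no causality, or calls it not assessable, the sponsor treats the event as associated.

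Section 8.2.3 repeats the exemption for deaths coded to progression, with no exception for those rated as associated. Section 10.3.7.1 tabulates treatment-emergent events by system organ class and preferred term for four subsets: serious, all, drug-related, and leading to discontinuation. It names no summary of fatal events or deaths.

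**The concern.** Sections 8.1.3 and 8.1.4 ask different questions. One asks whether the evidence is enough to suggest that the drug played a part. The other asks whether progression is the likelier explanation. Both answers can be yes for one death, and no section says what to do then. Applied as written, Section 8.1.4 decides the term and the reporting route without looking at the rating.

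Safety is the primary objective, the trial has no control arm, and the adverse event tables are built on preferred terms. A fatal toxicity shown as progression tells a reader of those tables nothing about which organ was harmed. An associated death that is labelled expected and not expedited also reaches regulators later than its rating would suggest.

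**Working it through.** No stated figure is at issue, so the check is a comparison of the sections, followed by one calculation for context.

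**1. Can both tests be met by one death?** Section 8.1.3 weighs alternative causes but does not require the drug to be the leading cause. Section 8.1.4 requires only that progression be the likelier one. A death with progression as the leading explanation and credible evidence of drug contribution meets both. So does a death judged more likely due to progression whose causality is left blank or called not assessable, because Section 8.1.3 then makes it associated by default.

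**2. What happens to that death?**

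| Step | Governing section | Result |
|---|---|---|
| Causality | 8.1.3 | Associated |
| Term for the fatal event | 8.1.4 | Malignant neoplasm progression |
| Number of fatal events | 8.1.4 | Generally one |
| Expedited reporting | 8.1.4, repeated in 8.2.3 | Exempt |
| Tabulation | 10.3.7.1 | Drug-related subset, under the progression term |

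The death is counted as drug-related, but the suspected toxicity is not named as the fatal event.

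**3. Is the overlap realistic for this drug?** Section 5.5.5 says that pneumonitis has been fatal, that a causal role for the drug could not be excluded, and that underlying pulmonary disease or cancer was among the confounders. Section 5.5.1 says that serosal effusions can be life-threatening and lists progression among the alternative causes to rule out. Section 5.5.4 reports fatal generalized edema. In advanced cancer these events are hard to separate from progression.

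**4. Scale, for context only.** Section 1.4 reports 104 treated subjects and 6 fatal AEs, "2 of which were considered related to rovalpituzumab tesirine (acute kidney injury and tumor hemorrhage").
- Related fatal rate: 2/104 = 1.9% (exact 95% interval 0.2% to 6.8%).
- Expected in a cohort of about 25 subjects (Section 10.1): 25 × 2/104 = 0.48.
- Chance of at least one: 1 − (102/104)^25 = 38%.

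This assumes that a rate from SCLC and LCNEC subjects carries over to the present cohorts. It shows that a cohort's fatal-toxicity profile may rest on no deaths or one, so the term given to a single death matters. It does not show how many would be mis-termed. That depends on the share of associated deaths for which progression is judged more likely, which the documents do not give and which could lie anywhere from 0 to 1.

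**The case against.** The strongest reply is that Section 8.1.4 chooses a term and a reporting route and does not switch off Section 8.1.3. The progression SAE still gets a causality rating, missing causality defaults to associated, and an SAE rated as having no reasonable possibility needs another stated cause. This stands. A reader might infer that counts of drug-related deaths are biased downward, but the documents do not support that: an associated death stays in the drug-related subset.

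Earlier events are also protected. Section 8.1.5 collects all AEs in the window, Section 8.1.2 requires a new entry when an event worsens, and Section 8.1.1.3 lets only symptoms of progression be subsumed. A toxicity already reported before death keeps its entry. What is at risk is its link to the fatal outcome, and the term itself where the toxicity first appears as the fatal event.

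Two other strong readings also fail. A reader might infer that the label carries into the dose-limiting toxicity review. Section 3.1.3 has its own test there, "clearly determined to be unrelated to study drug (e.g., PD"), limited to the first 3 weeks of Part A, and a progression term does not satisfy it. A reader might also infer that the tumor hemorrhage death in Section 1.4 would have been relabelled. It was reported under its own term and as related, and the documents do not say which coding rule applied to it.

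Finally, Section 10 leaves further analysis detail to a separate SAP. A death listing may be planned there, so the statement here is only that Section 10.3.7.1 does not name one.

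None of this tells a site which term to use when both tests are met, or removes the exemption for an associated death.

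**Conclusion.** The point holds in a limited form. Sections 8.1.3 and 8.1.4 are not reconciled for deaths in which progression is more likely but drug contribution is a reasonable possibility. Following the text places such a death under an uninformative preferred term in the primary safety data and exempts it from expedited reporting although it is associated.

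The number of deaths affected cannot be derived. It might be tempting to model all in-window deaths from the SCLC survival figures in Section 1.2. That would count every death rather than those meeting the rule, would borrow survival from a tumor type that this trial excludes, and would still need an unsourced share for mixed-cause deaths. The conclusion therefore rests on the wording of the sections and on the described toxicities, not on a projected count. This is a cheap improvement to the plan.

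**What to change.** - In Section 8.1.4, and in the matching exemption in Section 8.2.3, limit the progression term and the expedited-reporting exemption to deaths that are attributed to progression **and** rated No Reasonable Possibility under Section 8.1.3.
- For every other death in the AE reporting period, record the specific suspected fatal event with its own causality rating.
- Add to Section 10.3.7.1 or the SAP a listing of all in-window deaths by recorded term, cause and causality.

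The condition should not also require documented progression. That would deny the progression term to clinically evident cancer deaths that occur before a scan, and so create the opposite miscoding.

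The cost is protocol and CRF-guideline wording and one listing, with no extra subjects or procedures. The downside is that a few more deaths will be recorded under specific terms and will be subject to expedited reporting.
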